2.3.6. Medication Compliance

Since subjects are comatose and will be given study drug by endotracheal tube (ETT) over 12h compliance will be directly observed and verified by study team member in the research record. Thus, we anticipate 100% compliance unless study drug is stopped by a surrogate upon notification or for safety reasons both of which are unanticipated events.

2.3.7. Medication Storage and Accountability

Please refer to package insert of INOmax Nitric Oxide gas from INO Therapeutics/ Mallinckrodt for information on storage and accountability (cross reference authorized to NDA 20-845). Once delivered gas cylinders will be secured in a temperature controlled area within the respiratory therapy department. Gas cylinders (one blinded placebo and one blinded iNO) will be mounted on iNOvent delivery devices which will be stored within the emergency department to permit

rapid deployment. The contents of iNO after each use (in psi) will be documented and the cylinders will undergo high flow calibrations monthly and low flow calibrations weekly. Logs will be maintained on clipboards connected to the iNOvent.

2.3.8 Concomitant Medications

The following agents will not be permitted during study drug dosing: PDE5 inhibitors (sildenafil, vardenafil, tadalafil), sGC stimulators (riociguat), other nitrates (nitroglycerin, nitroprusside, isosorbide mono- and di-nitrate). PDE5 inhibitor and sGC stimulator use is cause for exclusion and these drug in general are seldom used within our population. We will likewise exclude subjects known to have the diagnosis of chronic thromboembolic pulmonary hypertension (CTEPH), pulmonary arterial hypertension (PAH) and erectile dysfunction which are the primary indications for PDE5 inhibitor and sGC stimulator use.

2.3.9 Rescue Medications

Hemodynamics will be stabilized using standard inotropic and vasopressor agents as needed in the ICU. There is no specific reversal agent for iNO. Methemoglobinemia can be reversed with treatment using methylene blue.

2.4 STUDY ENDPOINTS

Primary

Composite of in-hospital death, unfavorable discharge location, NYHA class III/IV heart failure at the time of discharge*

*In the setting of pre-existing heart failure or prior residence in an unfavorable location there must be at least a 1 class decrement (eg NYHA III -> IV)

Secondary

Functional

- Survival to hospital discharge, 30 and 90 days after initial OHCA
- Favorable cerebral performance category (CPC) defined as 1 or 2 at discharge, 30 and 90 days after initial OHCA
- Favorable modified Rankin score (mRS) defined as 0-3 at discharge, 30 and 90 days after initial OHCA
- Favorable discharge destination or location of residence (30 and 90 days after OHCA) defined as home or acute inpatient rehabilitation
- CPC-E at hospital discharge, 30 and 90 days after initial OHCA
- Barthel Index of Independence in Activities of Daily Living (ADL) at discharge, 30 and 90 days after OHCA

Neurologic

- Estimated likelihood of good neurologic outcome (0-100%) assessed by an experienced (>3y) member of the PCAS team blinded to treatment assignment on day 3-5 post-ROSC.
- Development of malignant EEG during hospitalization

- Time (in hours) to awakening from ROSC; defined as following commands (all values > 96h assigned 100)
- FOUR Motor + Brainstem scores on days 1-3 (requires 30 min off sedation; exclude endpoint if not medically permitted to pause sedation or paralysis)
- Presence or absence of upper and lower extremity somatosensory evoked potential N20 on comatose patients obtained any time after post-arrest day 1.
- Absolute value 24h after ROSC and change in value (24h vs 0h) of neuron specific enolase (NSE)
- EEG burst suppression ratio and change in suppression ratio
- EEG presence of dominant continuous background and reactivity to photic or tactile stimulation.

Cardiovascular

- Heart rate and mean arterial pressure (preferably off the arterial line) at 0-12 (hourly), 24h of study drug
- Persistent need for vasopressors in the first 24h after ROSC; defined as any use of norepinephrine, epinephrine, phenylephrine, dopamine or vasopressin for ≥ 3 h after study drug is initiated
- Persistent need of inotropes in the first 24h after ROSC; defined as any use of epinephrine, dobutamine, milrinone or isoproterenol for ≥ 3 h after study drug is initiated.
- ECHO measures (absolute values at end of therapy (12h) and change in 12h vs 0h):
 - tricuspid valve regurgitant velocity (TRV)
 - cardiac output based on aortic valve velocity (AV)
 - tricuspid annular plane systolic excursion (TAPSE)
 - left ventricular ejection fraction (EF).
- Absolute value at end of therapy (12h), change in value (12h vs 0h) and peak 24h post-ROSC troponin I
- Arterial blood gases at 0, 6, 12 and 24h after study drug initiation (when available)
- Upper body central venous oxygen saturation at 0, 6, 12 and 24h after study drug initiation (when available)
- Lactate at 0, 6, 12 and 24h after study drug initiation

Biochemical

- NO metabolites. Plasma nitrite, S-nitrosothiols and cyclic guanosine monophosphate (cGMP) levels obtained at 0, 3, 6, 9, 12h of study drug and 12h after cessation.
- RBC pellet for hemoglobin (Hb) studies (retained from above)
- MetHb at 6h (safety endpoint)
- Platelet mitochondria. Oxygen consumption rate, respiratory control ratio and superoxide generation (MitoSOX) at 0 and 12h of study drug when available. This data will be collected only when patients are enrolled from 6a-6p on weekdays (70/130 budgeted) to assure quality.
- Plasma for ascorbate 0, 3, 12, 24h
- Cardiolipin at 0, 3, 12, 24h
- After obtaining separate informed consent (IC) banked blood for DNA (pharmacogenetics)
- LSCI coupled to 1 and 5 min forearm vaso-occlusion at 0 h and 11 h. Endpoints will include ischemic trough, time to RH and RH peak, blood flow nadir 1 and 5 min after cuff release (respectively).

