The following data elements will be collected during the course of the study at the times indicated. Data elements marked with an asterisk indicate variables or outcomes essential for conduct of the study and analysis of efficacy and/or safety. These data elements should be obtained in all subjects with no missing data expected. In addition to these data elements, we are collecting a large amount of secondary data intended for use in mechanistic studies and hypothesis generation. In many cases, these data elements WILL NOT be able to be collected in all subjects. Such missing data will be handled as designated within an a priori statistical analysis plan but the presence of missing data will in no way impede our ability to meet the objectives of this phase 2 RCT.

BASELINE DATA

- *Date of OHCA
- *Time of OHCA (If not available we will use Time of ROSC after subtracting estimated no flow and CPR time based on transfer records/physician report)
- Witnessed
- Bystander CPR
- EMS Call Date
- EMS Call Time
- EMS Arrival Date
- EMS Arrival Time
- No flow time
- CPR (low flow) time
- Presenting rhythm
- *Date and Time of ROSC (If not available we will use ED admission date/time from referring hospital record. If unavailable, stat medevac call date/time minus 30 mins. If unavailable, time of arrival minus 15 min)
- PCAS ID
- *Last name
- *First name
- *Date of Birth
- *Medical record number
- Marital status
- Race/Ethnicity
- *Male Sex
- *Height
- *Weight
- Post-resuscitation chest pain

- Charlson Comorbidity
- Age Adjusted for Charlson Comorbidity Index (CCI)
- *New York Heart Association (NYHA) class pre-OHCA (if no surrogate is present and no medical records are found on the subject this will be assumed to be NYHA class I)
- Barthel ADL pre-OHCA
- Education level
- Private insurance
- Medicare
- Medicaid
- Employed
- Active smoker
- Smoker >20 pack-years
- Prior stroke
- Prior Coronary artery bypass grafting (CABG)
- Noninsulin-dependent diabetes mellitus (NIDDM2) type 2
- Insulin-dependent diabetes mellitus (IDDM2) type 2
- Diabetes mellitus (DM1) type 1
- Prior myocardial infarction (MI)
- Congestive Heart Failure (CHF)
- Chronic Obstructive Pulmonary Disease (COPD)
- Prior cardiac arrest
- Dementia
- Hyperlipidemia
- Hypertension
- Prior coronary stent
- Obstructive sleep apnea
- Pulmonary hypertension
- *Location pre-OHCA

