- *Best estimate of CPC pre-OHCA (if no surrogate is present and no medical records are found on the subject this will be assumed to be CPC 1)
- *Best estimate of mRS pre-OHCA ((if no surrogate is present and no medical records are found on the subject this will be assumed to be mRS 0)
- Rib fracture after ROSC
- Sternal fracture
- Witnessed aspiration
- Infection present at baseline
- Infection type
- Sputum color
- Vent mode
- Set Tidal Volume (V_t) or Inspiratory Pressure (P_{insp})
- Positive end expiratory pressure (PEEP)
- Fraction of inspired oxygen (FiO₂) expressed as % oxygen
- Peak Pressure (PIP)
- Plateau Pressure (P_{plat})
- Chest X-Ray reading possibly consistent with pneumonia
- Positive airway culture

Toxicology report

Cause of arrest

History of drug/alcohol use

Current drug/alcohol use

- ECHO RESEARCH ONLY To be performed by PCAS physician or research assistant trained by [name], who is a cardiologist and Associate Professor of Medicine at the University of Pittsburgh.
 - o Tricuspid valve regurgitant velocity
 - o Aortic valve velocity (CO estimate)
 - o Pulmonary valve velocity
 - o Tricuspid annular plane systolic excursion (TAPSE)
 - o LVEF
- *LSCI RESEARCH ONLY To be performed by a research assistant trained by the PI. A complete description is available in section CS10.1.
 - o Baseline blood flow and RH after 1 min vasoocclusion [resolution 1 image/s; 10 image/s averaging]
 - o Baseline blood flow and RH after 5 min vasoocclusion [begin 5 min after last test]*
 - *Baseline labs (troponin, arterial blood gas, lactate, plasma nitrite level,)
 - Additional plasma labs (neuron specific enolase, platelet mitochondria, ascorbate, cardiolipin, SNO, cGMP, plasma banking)
 - Urine labs (renal failure and nitrated fatty acid measurements)
 - Blood for genomics (retained unless informed consent declined)
 - *Baseline vital signs VS (temperature, heart rate [HR], mean arterial blood pressure [MAP], arterial oxygen saturation [SpO2])

STUDY DRUG (0-12 h) DATA

(Refer to Chart below)

- *Every 3 hour vital signs VS (temperature, HR, MAP, SpO2)
- Hourly monitoring of VS, SAEs, vent settings
- Pulmonary Arterial Pressures (systolic, diastolic, mean) – often not available
- Central Venous Pressure – often not available
- SvO2 – often not available
- *Plasma labs at 6 and/or* 12 h (troponin, arterial blood gas, lactate, methemoglobin, plasma nitrite level)

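### The secondary location endpoint lacks the prior-residence allowance that the primary makes, and the CPC and mRS secondaries make no use of the pre-arrest values collected

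*Combined protocol and SAP*

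**What the plan says.** Section 2.4 (repeated in the synopsis) sets three functional secondaries by fixed thresholds:

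- CPC: "Favorable cerebral performance category (CPC) defined as 1 or 2 at discharge, 30 and 90 days after initial OHCA".
- mRS: "Favorable modified Rankin score (mRS) defined as 0-3 at discharge, 30 and 90 days after initial OHCA".
- Location: "Favorable discharge destination or location of residence (30 and 90 days after OHCA) defined as home or acute inpatient rehabilitation".

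None refers to the subject's state before the arrest. The footnote to the primary composite, in the same section, does: "In the setting of pre-existing heart failure or prior residence in an unfavorable location there must be at least a 1 class decrement". It covers heart failure class and residence, and it is attached to the primary only.

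The baseline list in section 2.2 collects pre-arrest location, "Best estimate of CPC pre-OHCA" and "Best estimate of mRS pre-OHCA", all with an asterisk. If there is no surrogate and no record, CPC is taken as 1 and mRS as 0.

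Section 2.5.2 compares secondary dichotomous outcomes by chi-squared or exact tests. Its one adjusted binary model is a logistic regression, used only if confounders prove unbalanced and described directly after the composite test. Sections 3.2 and 3.3 contain no criterion on pre-arrest CPC, mRS or residence.

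**The concern.** The primary accepts that return to a prior unfavorable residence is not a treatment failure. The secondary location endpoint scores the same return as a failure, so one survivor can be judged in opposite ways on the same item at discharge.

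For CPC and mRS the issue is sensitivity. A subject whose pre-arrest level was already beyond the cut-off is scored unfavorable in either arm even after full return to that level. Such subjects dilute the difference between arms. The primary contains no neurologic scale, so CPC and mRS are the dichotomized measures of brain function in this trial, and section 2.5.3 accepts improvement in any secondary clinical outcome as preliminary evidence of efficacy. The pre-arrest values needed to deal with this are already collected.

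**Working it through.** **1. Location, rule against rule.** Take a survivor who lived in a nursing facility, returns to it at discharge, and has no NYHA III/IV heart failure.

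- Primary: the footnote requires a worsening of at least one class. Return to the same facility is no worsening, so there is no location failure.
- Secondary: the destination is neither home nor acute rehabilitation, so it is unfavorable.

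This is the only like-for-like mismatch, because CPC and mRS are not components of the primary.

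**2. Who is affected on CPC and mRS.** Only subjects with pre-arrest CPC of 3 or worse, or mRS of 4 or worse. Those with pre-arrest CPC 2 or mRS 1-3 can still be favorable. CPC-E and Barthel have no cut-off and are not affected.

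**3. The plan's own power figure.** The only figures given are for the composite (section 2.5.1): control rate 80-85%, a reduction of about 23 points, 60 per arm, power above 80%. I take the 5% error rate as two-sided alpha, in line with the two-tailed p < 0.05 in section 2.5.2. With

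power = Φ{ (d − 1.96·√[2p̄(1−p̄)/n]) / √[p1(1−p1)/n + p2(1−p2)/n] }, where d = |p1 − p2| and p̄ = (p1 + p2)/2,

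power at n = 60 is 78.1%, 80.1% and 82.3% for control rates of 80%, 82.5% and 85%. The stated figure reproduces approximately. No rates or power are given for CPC, mRS or location.

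**4. Dilution, as an illustration.** Let f be the share of subjects whose pre-arrest state lies beyond the cut-off. They contribute no favorable outcomes if none ends better than before, so each arm's favorable rate becomes (1 − f) times the rate among the others, and the difference shrinks by the same factor. The documents do not give f; I assume 5-15%. The rates are also assumed, as complements of the composite rates: 1 − 0.80 = 20% v 1 − 0.57 = 43%, and 1 − 0.85 = 15% v 1 − 0.62 = 38%. With 65 per arm:

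| f | Rates from 20% v 43% | Difference (points) | Power | Power from 15% v 38% |
|---|---|---|---|---|
| 0 | 20.0% v 43.0% | 23.0 | 81.3% | 85.2% |
| 5% | 19.0% v 40.9% | 21.9 | 78.3% | 82.6% |
| 10% | 18.0% v 38.7% | 20.7 | 75.1% | 79.8% |
| 15% | 17.0% v 36.6% | 19.6 | 71.6% | 76.7% |

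This is about 3 points of power per 5% of subjects.

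**5. How much could be recovered.** Suppose f = 10% and return to the prior level counts as favorable. Power then depends on how the previously disabled subjects fare:

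| Assumed return to prior level (placebo v iNO) | Overall rates | Power |
|---|---|---|
| 20% v 43% (like the rest) | 20.0% v 43.0% | 81.3% |
| 10% v 20% | 19.0% v 40.7% | 77.8% |
| 5% v 10% | 18.5% v 39.7% | 76.4% |
| 10% v 10% (no effect) | 19.0% v 39.7% | 74.2% |

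The last row is below the 75.1% of the fixed cut-off. Even in the first row, few subjects change category: 65 × 0.10 × 0.20 = 1.3 on placebo and 65 × 0.10 × 0.43 = 2.8 on iNO.

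**The case against.** A fixed cut-off is a legitimate and easily compared definition, and labelling CPC 3 or mRS 5 favorable in the headline result would be hard to defend. That stands, and it is why the cut-offs should stay.

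The power figures rest on an assumed f and on rates borrowed from the composite. That also stands. The exclusion for a predicted likelihood of death above 95% (section 3.3) may lower f, and with expected mortality of 70-80% (section 6.4.5) most unfavorable outcomes will be deaths under either rule.

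Pre-arrest CPC and mRS are best estimates with optimistic defaults, and section 2.2 lets most baseline elements be gathered retrospectively. Any rule that refers to baseline inherits these weaknesses. This limits the remedy but does not remove the reason for it.

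A reader might also infer more than the documents support:

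- That the asterisk promises use in an efficacy endpoint. It marks "variables or outcomes essential for conduct of the study and analysis of efficacy and/or safety", but names, record number and height carry it too, so leaving pre-arrest CPC and mRS out of the analysis does not contradict the plan.
- That the primary and the CPC and mRS secondaries contradict each other. Neither scale is in the primary.
- That anyone with prior impairment can never succeed. This is too broad: milder prior disability can reach the cut-offs, and a facility resident sent to acute rehabilitation counts as favorable on location.
- That the comparison is biased. Randomization balances prior disability in expectation.

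**Conclusion.** The location mismatch is a plain inconsistency within section 2.4 and needs no assumption. For CPC and mRS, the plan leaves pre-arrest information unused, at some cost in sensitivity and clarity. Chance imbalance in prior disability is possible at 65 per arm, and section 2.5.2 does not clearly extend its conditional adjustment to these outcomes.

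The size cannot be fixed from the documents. The loss of about 3 to 10 points of power (81.3% to between 78.3% and 71.6%) holds only for f between 5% and 15% and for 20% v 43% among subjects able to reach the cut-off. It is fully recoverable by a return-to-baseline rule only if previously disabled subjects respond like the rest. The primary analysis is not affected, and section 2.5.3 treats the secondaries as preliminary evidence. The change is worth making because it is nearly free, not because the trial's conclusion depends on it.

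**What to change.** Amend sections 2.4 and 2.5.2 before unblinding:

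1. Apply the primary's prior-residence rule to the secondary location endpoint at discharge, 30 and 90 days. State how locations are ranked, since the footnote's one-class example is for NYHA only.
2. Keep CPC 1-2 and mRS 0-3 as the headline definitions, and pre-specify logistic regression of each on treatment and its pre-arrest value. Enter that value as a single ordered term or in collapsed categories. Separate categories would leave strata with almost no favorable outcomes and invite separation with 130 subjects.
3. Add a sensitivity analysis that counts survivors no worse than their pre-arrest CPC or mRS as favorable, with death always unfavorable.
4. Record pre-arrest values blind to treatment and, where possible, before the outcome is known. Report how many rest on the defaults.

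The cost is plan wording and a few extra analyses, with no new data item. The defaults of CPC 1 and mRS 0 will still miss some prior disability, so the correction is partial.

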2.5.2 Study Conduct Analysis

Continuous data will be summarized and compared using t-tests or a non-parametric equivalent should the normality assumption appear tenuous. Generalized linear mixed models, which account for non-independence of repeated assessments and endpoint structure, will be used to compare between iNO and placebo groups at multiple times. Analysis of the composite endpoint will be ascertained using an unadjusted two sample test of proportions with a type II error rate of 5%. In the event of imbalance of potential confounders after randomization an adjusted analysis will be performed using logistic regression with those unbalanced variables and treatment as the main effect of interest. Other secondary dichotomous outcomes will be summarized and compared by chi squared tests and appropriate exact methods should sample sizes be small. Time to event endpoints will be summarized by Kaplan Meir curves and compared using log rank tests. All tests will be two tailed with unadjusted $p < 0.05$ considered significant and performed using SAS 9.4.

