2.5.5 Handling Missing Data

Since our primary endpoint is ascertained at hospital discharge we expect no missing data though all analyses will be performed assuming a missing at random mechanism. No data imputation will be performed though standard sensitivity analyses, using standard missing data techniques may be used.

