6.4.5 Reportable Adverse Events

This is a high risk population in which numerous serious adverse events are expected. Indeed, all subjects will require mechanical ventilation, with >50% of subjects expected to require >50% FiO₂ and/or vasopressors during the first 24 h based on our prior data^{33,34} and expected mortality is 70-80%³⁵ as we are excluding non-comatose subjects. Thus numerous serious adverse events (SAE) are anticipated during the conduct of this study with a complete list provided below. In this context we define a SUAE as any SAE that occurs in the setting of MetHb > 10% which may thus be attributed to the study drug.

Expected SAE (with severity grade indicated)

- Non-central nervous system thrombosis, particularly in vessels accessed for endovascular devices, assessed as symptomatic venous or arterial thrombus documented radiographically or ultrasonographically. (Grade 3)
- Sepsis assessed as the presence of microbiologically proven, clinically proven, or suspected infection; presence of Systemic Inflammatory Response Syndrome (SIRS); and development of at least one organ dysfunction within the preceding 24 hours. Diagnosis of SIRS will require the fulfillment of at least two of the following criteria (Grade 4):
 - Hyperthermia ($\geq 38^{\circ}\text{C}$) (which will only be evident after active temperature control);
 - Tachycardia ($\geq 90 \text{ bpm}$);
 - Tachypnea ($\geq 20 \text{ breaths/min}$) or an arterial pCO₂ $\leq 4.3 \text{ kPa}$ (32 mmHg) or mechanical ventilation;
 - White blood cell count $\geq 12,000/\mu\text{L}$ or $\leq 4,000/\mu\text{L}$ or left shift in differential white blood cell count $\geq 10\%$.
- Expected organ dysfunctions after OHCA (which may accompany SIRS in sepsis as defined above or separately) will be defined as:
 - Acute encephalopathy not explained by psychotropic medication (or attributable to the cardiac arrest) [Grade 3];
 - Thrombocytopenia $\leq 100,000/\mu\text{L}$ or drop in platelet count $> 30\%$ within 24 hours not explained by hemorrhage (Grade 3);
 - Arterial hypoxemia with an arterial pO₂ $< 8 \text{ kPa}$ (60 mmHg) when breathing room air or an oxygenation index (paO₂/FiO₂ $\leq 200 \text{ mmHg}$) not explained by presence of a pulmonary or cardiac disease (Grade 4);

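### Time to awakening has no rule for patients who die before waking, and censoring or dropping them biases the comparison whenever the timing of early death differs by arm

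*Combined protocol and SAP*

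**What the plan says.** The synopsis and Section 2.4 define the endpoint in the same terms: "Time (in hours) to awakening from ROSC; defined as following commands (all values > 96h assigned 100". The cap applies to values above 96 h. Neither place says what value, if any, goes to a patient who dies comatose at, say, 30 h.

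Section 2.5.2 offers two routes and names this endpoint under neither:
- "Time to event endpoints will be summarized by Kaplan Meir curves and compared using log rank tests"
- "Continuous data will be summarized and compared using t-tests or a non-parametric equivalent should the normality assumption appear tenuous"

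On significance it adds: "All tests will be two tailed with unadjusted $p < 0.05$ considered significant".

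Section 2.5.5 says that "all analyses will be performed assuming a missing at random mechanism", and continues: "No data imputation will be performed though standard sensitivity analyses, using standard missing data techniques may be used".

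Section 6.4.5 states that "expected mortality is 70-80" per cent. It does not say how much of that mortality falls before 96 h.

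Section 2.5.3 treats improvement in any secondary clinical outcome as preliminary evidence of efficacy, to be confirmed in a larger trial.

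**The concern.** Death before awakening is likely to be common in this population, so the handling of these patients could drive the result. Survival is listed at fixed time points. That leaves time to awakening as the only clinical endpoint worded as a time to an event, and the Kaplan-Meier and log-rank route is its natural home. By default that method censors a death at the time of death. It then assumes that the dead would have gone on to wake at the rate of those still alive and comatose. After cardiac arrest, severe brain injury leads both to death and to failure to wake, so that assumption is not credible.

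The hypothesis in Section 1.2 is that iNO reduces death, so a difference in the timing of death between arms is something the trial hopes to see. A real survival effect could then appear as apparent harm on awakening, and hastened death could appear as benefit. A rule left unstated can also be chosen after the data are seen.

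**Working it through.** The plan gives no power, effect size or expected rate for this endpoint, so there is no figure of its own to reproduce.

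**Inputs from the documents.** 130 subjects randomised 1:1, so 65 per arm (Section 2.1). Two-sided 0.05, so 2.5% in each direction (Section 2.5.2). Cap at 96 h (Section 2.4).

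**Assumptions, not in the documents.** 25% of each arm truly wakes by 96 h, at times uniform over 12 to 96 h. A stated share of non-wakers dies early. A patient whose death is delayed still does not wake by 96 h. True awakening is therefore identical in both arms, and any excess of significant results is error.

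**Step 1: the Kaplan-Meier curve.** With deaths censored, the curve estimates 1 − exp(−∫ f(t)/S(t) dt). Here f is the awakening density, 0.25/84 = 0.002976 per hour, and S(t) is the share still alive and not awake. Take early deaths uniform over 6 to 60 h.

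*50% of non-wakers die early* (0.75 × 0.50 = 37.5% of the arm):
- S(12) = 1 − 0.375 × 6/54 = 0.9583; S(60) = 1 − 0.25 × 48/84 − 0.375 = 0.4821; S(96) = 1 − 0.25 − 0.375 = 0.375.
- From 12 to 60 h, S falls by 0.002976 + 0.375/54 = 0.009921 per hour. The integral is (0.002976/0.009921) × ln(0.9583/0.4821) = 0.206.
- From 60 to 96 h only awakenings reduce S. The integral is ln(0.4821/0.375) = 0.251.
- The curve reads 1 − exp(−0.457) = 37% awake. The truth is 25%.

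*25% of non-wakers die early* (18.75% of the arm): S(12) = 0.9792, S(60) = 0.6696, S(96) = 0.5625. The integrals are 0.175 and 0.174, and the curve reads 1 − exp(−0.350) = 29.5%.

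Two arms with identical awakening would therefore be plotted at about 37% and 29.5%.

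**Step 2: the log-rank test, deaths censored.** Simulation under the same model, 2,000 to 3,000 trials per scenario:

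| Non-wakers dying early, placebo vs iNO | Trials wrongly significant in the biased direction |
|---|---|
| Equal shares | 2.3–2.6% |
| 30% vs 20% | 4.4% against iNO |
| 40% vs 30% | 4.5% against iNO |
| 50% vs 40% | 5.1% against iNO |
| 50% vs 25% | 10–11% against iNO |
| 25% vs 50% | 10% in favour of iNO |

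**Step 3: the other route.** If the endpoint goes to a rank test and early deaths have no value, they drop out. In this table deaths are uniform over 4 to 96 h and shares are of the whole arm, so rows do not line up with Step 2. Entries are the percentage of trials declaring iNO worse:

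| Early death, placebo vs iNO (whole arm) | Log-rank, deaths censored | Rank test, deaths left out | Rank test, deaths scored 100 |
|---|---|---|---|
| 40% vs 40% | 2.7 | 2.8 | 2.8 |
| 30% vs 15% | 4.7 | 8.6 | 2.4 |
| 40% vs 20% | 8.0 | 17.1 | 2.3 |

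Without a death rule, the continuous-data route is the more exposed of the two. Scoring deaths as 100 returns the error rate to about nominal.

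**Step 4: the role of the cap.** Suppose every patient still comatose is entered as an event at 100 h. With n at risk, n₁ of them on iNO, all n have the event. Expected events on iNO are n × n₁/n = n₁, equal to the observed number, and the variance term contains (n − n) = 0. The log-rank statistic does not move. The plotted curve does: it shows every remaining comatose patient waking at 100 h.

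**The case against.** The strongest reply is that the plan never says early deaths are censored. A reader might infer that it does, but the time-to-event sentence in Section 2.5.2 names no endpoint and gives no censoring rule. Censoring at death is the method's default, not the protocol's instruction. A score in hours with late values set to 100 also fits the continuous-data route, and a sympathetic reader could take the cap to cover anyone who never wakes, including the dead. On that reading no bias arises. All of this stands, and it limits the point to a missing rule. It does not remove it, because no section states the sympathetic reading and the continuous-data route without a death rule is worse (Step 3).

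A reader might also infer that the cap of 100 conflicts with the log-rank test and causes the bias. It does not: Step 4 shows that it leaves the statistic unchanged. Only the missing death rule matters for the test.

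A third tempting reading is that false harm runs at 20% or more. Simulation does give 21–23% at 60% versus 20% of non-wakers. With 25% waking, that means early death in 45% versus 15% of the arm. This 30-point difference exceeds the reduction of about 23% in the composite for which Section 2.5.1 sizes the trial (taking that as percentage points). The exclusions in Section 3.3 (haemodynamic instability, cerebral edema, malignant EEG, expected death above 95%) may also remove some early deaths. The documents do not support such a figure as the expected size.

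Finally, Section 2.5.3 calls a secondary improvement only preliminary, and favourable CPC and mRS are compared as proportions, where censoring does not arise. That is correct and lowers the stakes.

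**Conclusion.** The concern holds as a gap with a predictable consequence. The plan has no rule for death before awakening and does not name the test for this endpoint. Each of its two routes, followed by default, gives a biased comparison when the timing of early death differs by arm. The direction is clear: delaying death without changing awakening looks like harm, and hastening it looks like benefit.

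The size is uncertain. Under the stated assumptions the one-sided log-rank error is about 5% at a 10-point contrast among non-wakers and about 10% at 50% versus 25%, against 2.5%. With equal shares the test is unbiased, although the Kaplan-Meier curve still overstates awakening in both arms. These figures rest on early-death and awakening rates that the documents do not give, and on delayed deaths remaining unawakened to 96 h.

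The endpoint is secondary and the primary analysis is untouched. The change should still be made, because the default reading of the stated method gives a wrong answer in a trial that hypothesises fewer deaths.

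**What to change.** In Section 2.4 and the synopsis, state that any subject not following commands by 96 h after ROSC, alive or dead, is scored 100. In Section 2.5.2, name the endpoint and state that arms are compared by the Wilcoxon rank-sum test.

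An alternative that handles deaths in the same way is to keep them in the risk set to 96 h as not awake, and to plot the cumulative incidence of awakening with death as a competing event. In either case, do not plot 100 as an awakening time.

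The cost is about two sentences. Time to following commands and date and time of death are already on the data list in Section 2.2. The first item sits under a heading for 0 to 72 h, so confirm that it is recorded through 96 h. The small downside is interpretive: the result is read as a rank, or as being awake and alive, and not as a hazard of waking among survivors. If scoring deaths as 100 was always intended, the change simply writes it down before the data are seen.
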